6.5 COMMON CALCULATIONS

For quantitative measurements, change from baseline will be calculated as:

Value at Visit X – Baseline Value

Percent change from baseline will be calculated as:

$$\frac{\text{Value at Visit X} - \text{Baseline Value}}{\text{Baseline Value}} \times 100.$$

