For each visit, the least-squares mean (LSM) estimate, standard error, and 95% CIs will be presented for each treatment group. The least square mean difference of the treatment from placebo estimate, standard error, 95% CI, effect size, and p-value for each visit will also be presented in this table. The effect size is calculated as the difference in the LS mean estimate divided by the pooled estimate of within subject standard deviation obtained from the variance-covariance matrix used in the model. Descriptive statistics for the WOMAC pain score and change from baseline in WOMAC pain score will be presented in a table by visit and treatment group.

Additionally, if the normality assumption is not supported by the data, an analysis of covariance (ANCOVA) on rank-transformed data will be used as utility analysis and additional supportive analyses may be performed if necessary.

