16.1.5 SENSITIVITY ANALYSIS OF PRIMARY EFFICACY VARIABLE

Further details of sensitivity analyses are provided in [Appendix 3](#).

Sensitivity analyses will be performed to assess the impact of assumptions about missing data patterns on the primary and key secondary efficacy inferences. Additional analysis due to intercurrent events occurring in the trial will be performed.

The intercurrent events are defined as:

1. Discontinuation due to reasons related to study treatment (e.g. AE, LOE, lack of compliance, deviation from protocol, etc.),
2. Rescue medication drug use within 24 hours of WOMAC pain assessment,

Noven Pharmaceuticals, Inc.

Protocol HP-5000-US-07

3. Removal/detachment of the patch for more than 24 hours before WOMAC pain assessment.

Table B provides details on how these intercurrent events will be used for the sensitivity analyses.

Table B: Sensitivity Analysis Methods for Intercurrent Events

Analysis	Endpoint	Methods for Intercurrent Events		
		Discontinuation related to Study Medication	Rescue Medication	Patch Removal/ Detachment
Primary Efficacy	Mean change in WOMAC pain score from baseline to Week 12	1. Pattern Mixture Model	1. Pattern Mixture Model	1. Pattern Mixture Model
		2. Copy Reference Model	2. Copy Reference Model	2. Copy Reference Model

Pattern-Mixture Model and Copy Reference Sensitivity Analyses of MMRM Approach:

Robustness of the primary results under MNAR (Missing not at random) mechanisms will be assessed using pattern-mixture model and copy reference imputation approaches. All sensitivity analyses will be based on the pattern mixture model using multiple imputation for the dropout reasons and their assumed pattern of missing data as follows:

- LOE as MNAR with other missing data as MAR
- LOE and AE as MNAR with other missing data as MAR
- Any reason (all dropout) as MNAR

a. Multiple Imputation: Pattern Mixture Model (PMM)

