16.3 OTHER SECONDARY EFFICACY

Other secondary efficacy analyses will be performed for the ITT Set. For each below secondary efficacy variable, tables will be produced that display descriptive and inferential statistics by visit and treatment group. For continuous change from baseline variables descriptive and inferential statistics, comparable to those described in [section 16.1.3](#) for the primary efficacy variable will be presented. With no adjustment for intercurrent events.

For the secondary variables expressed as proportion of subjects with a response that is categorized as binary a logistic regression model will be used to obtain the point estimate of the odds ratio between treatment groups (HP-5000 and placebo) and the associated 95% confidence interval.

16.3.1 WOMAC LK3.1 OA (PAIN) CHANGE FROM BASELINE AT WEEKS 1, 2, 4, AND 8

The change from baseline will be analyzed using a MMRM analysis. As described in [section](#)

Noven Pharmaceuticals, Inc.
Protocol HP-5000-US-07

[16.1.3](#) for the WOMAC pain score, the same MMRM model will be applied.

A plot of the LS Mean change from baseline by visit will be presented.

16.3.2 WOMAC LK3.1 OA (PHYSICAL FUNCTION) CHANGE FROM BASELINE AT WEEKS 1, 2, 4, AND 8

The change from baseline will be analyzed using a MMRM analysis. As described in [section 16.1.3](#) for the WOMAC physical function score, the same MMRM model will be applied.

A plot of the LS Mean change from baseline by visit will be presented.

16.3.3 WOMAC LK3.1 OA (STIFFNESS) CHANGE FROM BASELINE AT WEEKS 1, 2, 4, AND 8

The change from baseline will be analyzed using a MMRM analysis. As described in [section 16.1.3](#) for the WOMAC stiffness score, the same MMRM model will be applied.

A plot of the LS Mean change from baseline by visit will be presented.

16.3.4 WOMAC LK3.1 OA (COMPOSITE SCORE) CHANGE FROM BASELINE AT WEEKS 1, 2, 4, AND 8

The change from baseline will be analyzed using a MMRM analysis. As described in [section 16.1.3](#) for the WOMAC composite score, the same MMRM model will be applied, with no adjustment for intercurrent events. The WOMAC Composite score is calculated by finding the total of the scores for the 3 subscales, WOMAC pain, WOMAC physical function and WOMAC stiffness, and then dividing by 96. Higher scores on the WOMAC indicate worse pain, stiffness, and functional limitations.

16.3.5 CHANGE FROM BASELINE IN PAIN INTENSITY ASSESSED ON AN 11-POINT NRS AT WEEKS 1, 2, 4, 8, AND 12

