APPENDIX 2. SAS CODE

PROC MIXED:

```
ODS OUTPUT LSMEANS=LSEST DIFFS=LSDIFF COVPARMS=COVS;
PROC MIXED DATA = TEST COVTEST;
CLASS TREATMENT VISIT SUBJECT;
MODEL change in womac pain score = treatment visit treatment*visit baseline womac pain
score;
LSMEANS TRTPN*AVISITN / DIFF CL;
REPEATED VISIT / TYPE = UN SUBJECT = SUBJECT;
RUN;
```

PROC LOGISTIC:

```
proc logistic data="Test" descending;
where visit variable = a given number (e.g., 4)
class treatment / param=ref ;
model respond = treatment PGA baseline value;
run;
```

[REDACTED]

Noven Pharmaceuticals, Inc.

Protocol HP-5000-US-07

[REDACTED]

Statistical Analysis Plan

Page 56 of 58

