APPENDIX 3. IMPLEMENTATION OF SENSITIVITY ANALYSES AND ANALYSES FOR OTHER RELEVANT ESTIMANDS

Sensitivity analyses of the primary and key secondary efficacy endpoint will be performed to assess the impact of assumptions about missing data patterns on the primary inferences during the trial.

The change from baseline to Week 12 summary statistics will be presented for both imputation approaches described below. The dropout reason, shift value, treatment group, LS Mean difference values along with 95% CIs will be presented. Nominal p-values comparing the HP-5000 treatment group versus placebo will also be displayed.

a. Multiple Imputation: Pattern Mixture Model (PMM)

Step 0: Missing data will be imputed using a multiple imputation technique assuming MAR for all treatment groups.

Step 1: A shift ($\Delta 1$) will be added to all imputed data in Step 0 in the Placebo group to worsen imputed scores. The range of values $\Delta 1$ can be calculated from $\Delta 1=k1 \times$ the upper bound (UB1) where $k1=0, 0.33, 0.67$, and $1 \times$ the UB1 for $\Delta 1$. The UB1 will be based on the end point, UB1 for WOMAC Pain is 4, UB1 for WOMAC Physical Functioning is 12, and UB1 for WOMAC Stiffness is 2. The UB1's for $\Delta 1$ are selected to be reasonably higher than the SD estimated from the blinded data to provide a sufficiently wide range for the imputation. Note for WOMAC Pain $\Delta 1=0, 1.3333, 2.6667, 4$ for imputation purpose. For WOMAC Physical Functioning $\Delta 1=0, 4, 8, 12$. For WOMAC Stiffness $\Delta 1=0, .6667, 1.3333, 2$.

Step 2: A shift ($\Delta 2$) where $\Delta 2=\Delta 1+ k2 \times$ LS mean difference (LSMD) is also added to the imputed data in Step 0 in the active treatment group to worsen their imputed scores. For each value of $\Delta 1$, the value of $\Delta 2$ will be calculated using $k2 (k2=0, 0.2, 0.4, 0.6, 0.8 \text{ and } 1) \times$ LSMD between the active treatment group vs placebo based on the MMRM primary analysis. It is important to note that if $k2=0$, then $\Delta 2=\Delta 1$, and if $k2=1$, then $\Delta 2=\Delta 1+ LSMD$; therefore, the considered range for $\Delta 2$ is from $\Delta 1$ to $\Delta 1+ LSMD$. A total of 24 combinations of shifts will be added to the imputed values.

Step 3: The primary MMRM model is then applied to each of the complete datasets created from Step 0 through Step 2.

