Step 4: Step 0 through Step 3 are then repeated $m=100$ times and PROC MIANALYZE is then applied to combine the estimates using Rubin's combination rules.

Noven Pharmaceuticals, Inc.

Protocol HP-5000-US-07

Justification of the ranges of $\Delta 1$ and $\Delta 2$ values to cover the plausible domain of the missing values is supported by the following, using WOMAC Pain UB1. The $\Delta 1$ will assume a value ranging from 0 to 4. This UB1 of 4 for $\Delta 1$ is selected to be reasonably higher than 1 SD of the primary endpoint of the study and is used to cover wider range of imputations. For the case of the lower boundary of $\Delta 1=0$, the missing data in the placebo group are considered as MAR. For the case of upper boundary of the range of $\Delta 1=4$, the missing data in the placebo group are considered MNAR with a fixed worsening shift of 4 from the imputed values assuming MAR of all missing WOMAC data. Such a magnitude represents a reasonable upper bound for the range of deviation from MAR imputation. The boundaries of $\Delta 2$ are selected to start from $\Delta 2=\Delta 1$ to $\Delta 2=\Delta 1+LSMD$. With the starting values of $\Delta 2=\Delta 1$, MNAR data for discontinued subjects either from the active treatment group or the placebo group are worsened by the same shift from their imputed WOMAC total score based on MAR. With the upper boundary of $\Delta 2$ defined by $\Delta 2=\Delta 1+LSMD$, the MNAR data for discontinued subjects from the active treatment group will have their WOMAC imputed scores based on MAR worsened by larger amounts that are equal to the whole LSMD rather than a fraction of the LSMD (in addition to the $\Delta 1$).

b. Multiple Imputation: Copy Reference (Placebo) Approach

Step 0: Missing data in the placebo group are imputed using a multiple imputation technique assuming MAR.

Step 1: Missing data in the active treatment group are imputed based on the conditional distribution estimated from the placebo group using a multiple imputation technique.

Step 2: A range of common shifts ($\Delta=0, 1.3333, 2.6667, 4$ units – WOMAC Pain) are added to the imputed data in Step 0 for the placebo group and in Step 1 for the active treatment group to worsen imputed scores. ($\Delta=0, 4, 8, 12$ units – WOMAC Physical Functioning) ($\Delta=0, 0.6667, 1.3333, 2$ units – WOMAC Stiffness)

Step 3: The primary MMRM model is then applied to each of the complete datasets created from Step 0 through Step 2.

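### The pattern-mixture shift Δ2 = Δ1 + k2 × LSMD (SAP Appendix 3) has no sign rule and, under the SAP's own definitions, favours HP-5000 instead of stressing its result

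*SAP*

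**What the plan says.** SAP Appendix 3, part a, imputes missing WOMAC scores under MAR and then shifts them. Step 1 adds Δ1 to the placebo imputations; for pain, Δ1 is 0, 1.3333, 2.6667 or 4. Step 2 sets the active-arm shift to Δ2 = Δ1 + k2 × LSMD, with k2 = 0, 0.2, 0.4, 0.6, 0.8 or 1 and LSMD taken from the primary MMRM. The text says that the resulting multiple of the "LS mean difference (LSMD) is also added to the imputed data in Step 0 in the active treatment group to worsen their imputed scores". The justification that follows treats Δ1 + LSMD as the upper end of the range, where active-arm scores are "worsened by larger amounts that are equal to the whole LSMD rather than a fraction of the LSMD", on top of Δ1.

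The sign of LSMD has to be put together from other sections:

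- SAP 6.5 defines change as "Value at Visit X – Baseline Value".
- SAP 16.3.4 gives the direction of the scale: "Higher scores on the WOMAC indicate worse pain, stiffness, and functional limitations".
- SAP 16.1.3 reports "The least square mean difference of the treatment from placebo estimate" at each visit.
- The sample code in SAP Appendix 2 requests "LSMEANS TRTPN*AVISITN / DIFF CL" without giving the coding of TRTPN.

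SAP 16.1.5 states the scope of the sensitivity analyses: "assumptions about missing data patterns on the primary and key secondary efficacy inferences".

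**The concern.** The words and the formula point in opposite directions. A shift worsens a WOMAC score only if it is positive, and Δ1 + LSMD can be an upper boundary only if LSMD is positive. On the SAP's own definitions, LSMD is negative when HP-5000 works. Adding k2 × LSMD then lowers the active-arm shift, and no place in the SAP says to use the magnitude.

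The analysis is meant to ask whether the result survives if active-arm dropouts did worse than MAR predicts, by more than placebo dropouts did. As written, the grid never enters that region. For fixed Δ1, a larger k2 moves the estimate towards the drug, so the table could show robustness where the intended grid shows fragility. The formula serves pain, physical function and stiffness alike.

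**Working it through.** **Sign.** Improvement is a negative change, and the difference is HP-5000 minus placebo, so LSMD < 0 for an effective drug. All k2 values are non-negative and cannot reverse this.

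**The plan's own count.** 4 values of Δ1 × 6 values of k2 = 24 combinations, as Appendix 3 states. Of these, 4 × 5 = 20 have k2 > 0.

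**Direction of Δ2.** For any negative LSMD and any of the three endpoints:

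| | Δ2 < Δ1 | Δ2 = Δ1 | Δ2 > Δ1 |
|---|---|---|---|
| As written, k2 × LSMD | 20 | 4 | 0 |
| Intended, k2 × \|LSMD\| | 0 | 4 | 20 |

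**Cells where Δ2 < 0**, so that active imputations become better than MAR. The documents give no LSMD, so ranges are assumed.

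- Pain, LSMD −0.5 to −2.0: 5 to 7 of 24.
- Physical function, LSMD −1.5 to −6: 5 to 7 of 24.
- Stiffness, LSMD −0.2 to −0.8: 5 to 6 of 24.
- With |LSMD|: none.

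For pain with LSMD = −1.0 and Δ1 = 0, Δ2 is 0, −0.2, −0.4, −0.6, −0.8, −1.0. At Δ1 = 4 and k2 = 1, it is 4 − 1 = 3.0 as written and 4 + 1 = 5.0 as intended.

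**Effect on the estimate.** To first order, with missing fractions dA (active) and dP (placebo):

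estimate = LSMD + dA × Δ2 − dP × Δ1.

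At k2 = 1 the two readings differ by 2 × dA × |LSMD|. With LSMD = −1.0 that is 0.30, 0.40 and 0.50 points at dA = 15%, 20% and 25%.

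**Illustration for pain.** Assumptions: LSMD = −1.0; z = 2.80 (1.96 + 0.84, the expected value at the planned 80% power), so SE = 1.0 / 2.80 = 0.357; no allowance for the extra imputation variance. Worked cell, Δ1 = 4, k2 = 1, 20% active and 15% placebo missing:

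- As written: −1 + 0.20 × 3 − 0.15 × 4 = −1.00, p = 0.005.
- Intended: −1 + 0.20 × 5 − 0.15 × 4 = −0.60, z = 1.68, p = 0.093.

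| Missing, active / placebo | Cells losing significance: written | Intended | Δ1 = 4, k2 = 1: written | Intended |
|---|---|---|---|---|
| 20% / 20% | 0 of 24 | 0 of 24 | −1.20 (p 0.0008) | −0.80 (p 0.025) |
| 20% / 15% | 0 | 4 | −1.00 (p 0.005) | −0.60 (p 0.093) |
| 25% / 15% | 2 | 13 | −0.85 (p 0.017) | −0.35 (p 0.33) |
| 15% / 20% | 0 | 0 | −1.35 (p 0.0002) | −1.05 (p 0.003) |

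Cells with an estimate stronger than the primary result, as written: 20, 11, 8 and 23 in the four rows. On the intended grid they are 0, 0, 0 and 14. The 14 arise because, with more placebo data missing, the common shift Δ1 itself widens the difference.

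**The case against.** The strongest reply is that the prose already supplies the sign. The stated purpose is to worsen active scores, and the justification speaks of larger amounts and an upper boundary. A careful programmer would take the magnitude, so on this view only a symbol is missing. That is right about intent, but Appendix 3 is the implementation specification, and a literal coder and a careful coder would produce opposite analyses from it.

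Second, the subtraction order is not firmly fixed. Step 2 says only active versus placebo, and the sign from the SAS code depends on a treatment coding that is not given. If the code returned placebo minus HP-5000, LSMD would be positive and the formula would work. That would depart from the order given in SAP 16.1.3, and it confirms that no sign rule is stated.

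Third, Appendix 3 requires the shift values to be tabulated, so an active shift that is negative or below placebo's would be visible. That stands as a safeguard, but it operates only after unblinding.

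Fourth, the practical effect may be small. Significance counts differ only in the two scenarios with more missing data on active, whereas the one imbalance that SAP 16.1.5 discusses is lower discontinuation on active. The 15% to 25% fractions fit the pattern in which all dropouts are MNAR; the two narrower patterns (lack of efficacy, with or without adverse events) shift fewer values. With shifted fractions of 5%/5%, 10%/10% or 8%/5%, no cell loses significance under either reading. This limits the likely size but does not make the formula right.

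**Conclusion.** The concern holds: the formula is wrong as written. That Δ2 falls below Δ1 in 20 of 24 cells and exceeds it in none follows from the SAP's definitions for any negative LSMD. How far this would change the reported conclusions is uncertain. It rests on assumed values of LSMD, z and the missing fractions, and on a first-order calculation. In the scenarios tried, the number of cells that lose significance but would not appear to do so ranges from none to 11 (13 − 2). Only the pattern-mixture sensitivity analysis of the primary and key secondary endpoints is affected. It should be fixed before unblinding, but it does not threaten the primary inference.

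**What to change.** In Appendix 3 Step 2, and in the justification of the ranges, write Δ2 = Δ1 + k2 × |LSMD|. State that LSMD is HP-5000 minus placebo, that a positive shift means worsening, and that the range of Δ2 is Δ1 to Δ1 + |LSMD|. Fix the treatment coding or the order of the difference in the Appendix 2 sample code to match. It would also be tidy, though not essential, to say what is done if LSMD is zero or positive, for example running k2 = 0 only.

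The cost is one symbol and about two sentences of SAP text, with no new data and no additional runs.

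Separately, and not part of this point, the copy-reference shifts in Appendix 3 (for pain 0, 1.3333, 2.6667, 4) differ from the protocol's 1, 2, 4, 8, 12 in section 13.4.3.1, while SAP 3.3 records no changes from the protocol. One line there with the reason would close it.

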#### Pattern-Mixture Model and Copy Reference Sensitivity Analyses of MMRM Approach:

Robustness of the primary results under MNAR (Missing not at random) mechanisms will be assessed using pattern-mixture model and copy reference imputation approaches. All sensitivity analyses will be based on the pattern mixture model using multiple imputation technique for the dropout reasons and their assumed pattern of missing data as follows:

- Not Study Treatment Related or Uncertain reason for withdrawn as MAR
- Study Treatment Related reason as MNAR

- a. Multiple Imputation: Pattern Mixture Model (PMM)

The missing data due to early discontinuations will be imputed assuming MNAR following the approach described in Permutt (2016). That approach will be implemented by imputing missing

data first under the MAR assumption in each treatment group using multiple imputation and then adding a pre-defined  $\Delta 1$  to each imputed value in the placebo group and adding a different pre-defined  $\Delta 2$  to each imputed value in the active treatment group, then varying  $\Delta 1$  and  $\Delta 2$  over an enclosure of a plausible range of values. As noted in the article by Permutt (2016), this is considered the most appropriate kind of sensitivity analysis for the missing data problem. Also, this imputation approach was documented on Page 89 of the NRC report (2010).

b. Multiple Imputation: Copy Reference (Placebo) Approach

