3. STUDY DESIGN

3.1 GENERAL DESCRIPTION

This is a multicenter, randomized, double-blind, placebo-controlled Phase 3 study in the US

Noven Pharmaceuticals, Inc.

Protocol HP-5000-US-07

Statistical Analysis Plan

Page 14 of 58

evaluating the efficacy and safety of HP-5000 in subjects with OA pain of the knee.

The study will consist of up to a 28-day Screening Phase that will include a Washout Period of current prescription and over the counter (OTC) analgesics; a 12-week Double-blind Treatment Phase, and a 1-week safety Follow-up Phase.

Screening Phase: Subjects will be seen in the clinic where the study will be described to them and will be asked to sign the informed consent form (ICF). No screening procedures may begin prior to obtaining informed consent. After obtaining a written informed consent, subjects will be screened for participation in the study. The target knee for the purpose of the study will be defined as the one which causes the subject more pain than the other knee and will be identified at the Screening visit using the NRS score. During the Screening Phase, subjects will complete a daily electronic diary (eDiary) to record pain severity of their target knee. Subjects who satisfy the entry criteria will be instructed to begin the Washout Period for 7 to 14 days, or at least 5 half-lives, whichever is longer, prior to the Baseline Visit (Day 0).

During the Washout Period, current prescription and OTC analgesics will be discontinued. However, rescue medication (acetaminophen [APAP]) for the treatment of any other aches the subject might experience during the trial, such as headache, reduction of fever, and the target knee pain of OA (not for the non-target knee) will be permitted (a maximum of 2 g/day) except within 3 calendar days prior to the Baseline Visit (i.e., rescue medication is prohibited for 2 days until clinic visit on Day 0 and on the day of Baseline Visit [V3]). During the Washout Period, subjects will complete a daily eDiary to record rescue medication usage in addition to pain severity of their target knee. Following completion of the Washout Period, subjects will return to the clinic for their Baseline Visit (Day 0). Eligible subjects will be randomized to either HP-5000 or placebo in a 1:1 ratio.

Treatment Arm	Treatment
HP-5000	HP-5000 [REDACTED] patch Each patch contains [REDACTED] diclofenac sodium.
Placebo	HP-5000 [REDACTED] Placebo patch Each patch contains 0% [REDACTED] diclofenac sodium.

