Double-blind Treatment Phase: Subjects will apply a single patch to the target knee [REDACTED]

[REDACTED] After the removal of the patch [REDACTED], a new patch will be applied to a different site on the target knee. Subjects will be instructed to rotate the patch application site [REDACTED] to alternate sides (inner and outer) of the target knee. During the Double-blind Treatment Phase, subjects will also complete a daily eDiary to record patch application and removal time, adhesion, irritation, discomfort, and pain assessments; and

Noven Pharmaceuticals, Inc.

Protocol HP-5000-US-07

Statistical Analysis Plan

[figure not shown]
Page 15 of 58

amount of rescue medication (APAP) taken daily, if applicable. A maximum of 2 g/day of APAP will be allowed as rescue medication except from Baseline Visit until Visit 4, within 2 calendar days prior to all subsequent visits (V5, V6, V7, and V8), and on the day of the clinic visits (V4, V5, V6, V7, and V8).

NOTE: Subjects are NOT allowed to apply HP-5000 on the non-target knee at any time during the study.

Follow-up Phase: Subjects will have a safety visit approximately 7 days after the Week 12 End-of-Treatment Visit. The investigator or qualified study staff will contact all subjects by phone for continued safety monitoring of AEs. At the discretion of the investigator, subjects may have to return to the clinic for their Follow-up Visit.

Figure 1: A Schematic of the Study Design

Sample Size: Based on the HP-5000 Phase 2 study results, the assumed effect size of the test product in the pivotal study will be about [REDACTED]. The sample size of [REDACTED] subjects per treatment arm (or total of about [REDACTED] subjects) will be included in order to have 80% power to demonstrate statistically significant difference versus placebo using a 2-sided overall Type I Error rate of 0.05.

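### The HP-5000 shift in the pattern-mixture analysis is scaled to the trial's own estimated effect and capped there, so it is not pre-defined and, with balanced moderate dropout, can stop short of the tipping point.

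*SAP*

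**What the plan says.** Protocol 13.4.3.1, part a, imputes missing scores under MAR. It then adds a pre-defined Δ1 "to each imputed value in the placebo group and adding a different pre-defined" Δ2 to those in the active group, and varies both over a range meant to enclose what is plausible. SAP 16.1.5, part a, repeats this.

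SAP Appendix 3 gives the implementation. In Step 1 the placebo shift Δ1 is fixed in advance: "UB1 for WOMAC Pain is 4", with grid 0, 1.3333, 2.6667, 4. The upper bounds are 12 for physical function and 2 for stiffness. In Step 2, Δ2 = Δ1 + k2 × LSMD, with multipliers "k2=0, 0.2, 0.4, 0.6, 0.8" and 1, where the LSMD is the "LSMD between the active treatment group vs placebo based on the MMRM primary analysis". The appendix states that Δ2 therefore spans only Δ1 to Δ1 + LSMD, and its justification paragraph says so again. That paragraph also calls 4 points a reasonable upper bound for departure from MAR.

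Part b of the appendix adds a copy-reference analysis with shifts common to both arms. SAP 3.3 records no change from the protocol.

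**The concern.** A sensitivity analysis for missing data should test the result against departures from MAR chosen without reference to that result. Here the extra worsening on HP-5000 is a fraction, at most the whole, of the estimate being tested. Two things follow.

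- Δ2 is fixed as a formula but not as a number, which is not what the protocol and the SAP body describe.
- The 4-point departure that the SAP itself regards as plausible is never applied to HP-5000 dropouts while placebo dropouts stay at MAR, unless the LSMD itself reaches 4. In every planned cell Δ1 enters both arms.

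At stake is the meaning of a statement that the result held in all cells. With balanced dropout it may say little beyond what the primary p-value and the missing fraction already imply.

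**Working it through.** **Inputs from the documents.** Two-sided alpha 0.05 and 80% power (SAP 3.1); 1:1 allocation (SAP 3.1); the k1 and k2 values, the Δ1 grid and the source of the LSMD (SAP Appendix 3).

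**Assumptions.** The effect size and N are redacted. The SD is not given, although Appendix 3 implies it is below 4. No missing fraction is given. I use missing fractions of 10% to 30%, SD 3.5, and effect sizes 0.2, 0.3 and 0.5 (LSMD 0.70, 1.05 and 1.75 points). I take the LSMD as an absolute size, because Step 2 says the shift worsens scores. Under SAP 6.5 and 16.1.3 a beneficial LSMD is negative, so the formula read literally would improve them.

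**Plan's own figure.** 4 values of k1 × 6 values of k2 = 24 combinations, as stated.

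**Effect of the shifts.** Let E = |LSMD|, and let fa and fp be the fractions imputed and shifted on HP-5000 and placebo. The placebo mean worsens by fp × Δ1 and the HP-5000 mean by fa × (Δ1 + k2 × E). The remaining benefit is

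E × (1 − k2 × fa) − Δ1 × (fa − fp).

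With fa = fp = f, Δ1 cancels from the estimate, and the worst cell (k2 = 1) leaves (1 − f) × E.

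**Tipping point, equal missingness, SE unchanged.** With primary statistic z0, p reaches 0.05 at k2* = (1 − 1.96/z0)/f. At the design level z0 = 1.96 + 0.84 = 2.80, so k2* = 0.30/f. Only a primary z below 1.96/(1 − f) can tip inside the grid.

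| f | Worst-cell estimate | Worst-cell p at z0 = 2.80 | Tips only if primary p exceeds | k2* at z0 = 2.80 | Share of significant results overturned (80% power) |
|---|---|---|---|---|---|
| 10% | 0.90 E | 0.012 | 0.029 | 3.0 | 8% |
| 15% | 0.85 E | 0.017 | 0.021 | 2.0 | 14% |
| 20% | 0.80 E | 0.025 | 0.014 | 1.5 | 20% |
| 30% | 0.70 E | 0.050 | 0.005 | 1.0 | 37% |

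The grid stops at k2 = 1.

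**Unequal missingness** (E = 1.05, Δ1 = 4, k2 = 1):

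- 25% HP-5000, 15% placebo: penalty 0.25 × 5.05 − 0.15 × 4 = 0.66, leaving 0.39.
- 30% and 10%: penalty 0.30 × 5.05 − 0.10 × 4 = 1.12, more than the observed effect.
- 15% and 25%: penalty 0.15 × 5.05 − 0.25 × 4 = −0.24, so the estimate improves to 1.29.

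**Simulation check.** A Week 12 ANCOVA with multiple imputation and Rubin's rules stood in for the MMRM (effect size 0.3, SD 3.5, 15 imputations, 600 trials per setting, Monte Carlo error about 2 percentage points). With Δ1 = 4 and k2 = 1, the shares of significant results overturned were about 20%, 37% and 52% at 10%, 20% and 30% equal missingness. These exceed the closed form because the shift also inflates the variance. At 25%/15% missing the share was about 85%; at 15%/25% it was about 0.4%. At 20% missing with Δ1 = 0, raising the k2 limit from 1 to 3 raised the share from about 22% to 96%.

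**The omitted cell, Δ1 = 0 and Δ2 = 4, at 20% missing.** The penalty is 0.20 × 4 = 0.80. For E = 0.70, 1.05 and 1.75 this leaves −0.10, 0.25 and 0.95. The worst planned cell leaves 0.56, 0.84 and 1.40.

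**The case against.** The formula, the multipliers and the source of the LSMD are all fixed beforehand, so the analyst has no discretion. Appendix 3 argues for the range, and the p-values are labelled nominal. A second analysis, copy reference, uses shifts that do not depend on the LSMD. The first two points stand, but they do not make Δ2 a pre-defined value or widen its range. The third does not lift the limit, because the copy-reference shifts are common to both arms.

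A reader might go further and infer any of the following, which the documents do not support.

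- *The grid can hardly ever overturn the result, so robustness is guaranteed by construction.* The simulated shares above show otherwise for borderline results, high missingness or excess HP-5000 dropout. SAP 16.1.5 itself expects that discontinuation may differ by arm.
- *The between-arm penalty can never exceed the observed effect.* That holds for each imputed score, not for the arm means, as the 30%/10% case shows.
- *A weaker observed effect gets a milder test.* The shift is smaller in points, but with equal missingness the worst cell removes the same fraction f of the effect, and borderline results are the ones that tip.
- *The extreme cell merely repeats the zero-benefit composite rule.* SAP 16.1.4 does not say whether zero benefit is relative to placebo or to baseline. MAR imputation also conditions on earlier scores, so k2 = 1 can place HP-5000 dropouts below comparable placebo subjects.

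**Conclusion.** The point holds in a limited form. Δ2 is not pre-defined as a value, contrary to Protocol 13.4.3.1 and SAP 16.1.5, and its excess over Δ1 is capped at the observed effect. With balanced missingness and no variance inflation, the grid does not reach the tipping point of a design-level result until about 30% is missing. When the grid does overturn a result, that depends on the primary p, the amount of missing data and the direction of dropout imbalance, not on a range of departures chosen in advance.

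The primary estimate is unaffected, so this should be corrected but does not undermine the main analysis. The 30% figure needs only the stated alpha and power plus equal missing fractions. The figures in points and the simulated shares rest on the assumed SD, effect size and missingness.

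**What to change.** In Appendix 3, part a, Step 2, replace the LSMD-based Δ2 with fixed values in scale points. Cross Δ1 and Δ2 independently over the SAP's own grid:

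- pain: 0, 1.3333, 2.6667, 4
- physical function: 0, 4, 8, 12
- stiffness: 0, 0.6667, 1.3333, 2

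Include Δ1 = 0 with Δ2 at the upper bound, and report which (Δ1, Δ2) cells lose p < 0.05. This delivers what the protocol and SAP 16.1.5 already describe, and it removes the ambiguity over the sign of the LSMD.

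The crossed grid has 4 × 4 = 16 cells per endpoint. Four of them (Δ1 = Δ2) are the present k2 = 0 cells, so 12 are new. The cost is SAP wording and these extra imputation runs, and some cells will look less favourable. The grid will not always contain the tipping point: at 10% missing and E = 1.75, a design-level result would need 3.0 × 1.75 = 5.25 points. It would, however, test the range that the SAP itself calls reasonable.
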